9.8 Safety

The assessment of safety will be based mainly on the frequency of AEs that are treatmentemergent. Formal tests will not be conducted for differences in safety parameters between treatment groups.

The incidence of all treatment-emergent AEs will be after grouping by body system and preferred term. For each preferred term and summarized over each body system overall, the table will present the number of patients in each treatment group in whom the event occurred and the rate (%) of occurrence. The incidence of all suspected-drug-related AEs will be tabulated similarly. The incidence of all treatment-emergent AEs will also be tabulated by severity categories. The summary of all AEs by treatment groups will also be presented within subgroups by sex, age and race.

Safety will also be summarized with respect to vital signs and laboratory safety parameters as mean levels by visit and change from baseline. Laboratory values will be further summarized with shift tables. Abnormal observations on physical exams will be listed.

9.9 Sample size calculation

The calculation of 90 per treatment group is based on the following assumptions and considerations:

- □ Primary efficacy outcome is the change from baseline for POM at 72 hours after initiating treatment.
- \Box Two-sided t-test situation with $\alpha = 5\%$.
- \square Assuming SD = 20 mm, the sample size provides approximately 80% power to detect a difference of 10 mm between two treatment groups if 64 patients per group are analysed.
- □ However, the sample size will be stipulated to n=90 per group in order to power also the two subgroup comparisons.
- □ Moreover, the sample size will be a total of 200 patients because a dropout-rate of approximately 10 % is taken into account

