Study Objectives To determine efficacy and safety of a Esflurbiprofen Hy compared to placebo in patients with acute strains, sprains the extremities following blunt trauma, e.g. sports injuries.			

	To demonstrate that the Esflurbiprofen Hydrogel Patch is superior to placebo, and that the patch has acceptable local tolerability.			
Study Design Patient Population/Sample size/Study Sites	Randomized (1:1) (stratified by center and 2 subgroups), controlled, double-blind, multi-centric study in parallel groups. The clinical trial population will consist of male or female patients, 18 – 60 years suffering from acute; strains, sprains or bruises of the extremities following blunt trauma, and meeting all clinical trial entry criteria.			
	In order to ensure at least 90 evaluable patients per group, up to 200 patients will be enrolled (assumes a drop-out-rate of $\leq 10\%$).			
	The study will be performed in Germany in 3 sites. Each site should enroll a minimum of 30 and a maximum of 90 patients.			
Statistical Considerations	 enroll a minimum of 30 and a maximum of 90 patients. Samplesize The calculation of 90 per treatment group is based on the following assumptions and considerations: Primary efficacy outcome is the change from baseline for POM 72 hours after initiating treatment. Two-sided t-test situation with α = 5%. Assuming SD = 20 mm, the sample size provides approximate 80% power to detect a difference of 10 mm between two treatmer groups if 64 patients per group are analysed. However, the sample size will be stipulated to n=90 per group i order to power also the two subgroup comparisons. Moreover, the sample size will be a total of 200 patients becaus a dropout-rate of approximately 10 % is taken into account 			

Analysis

Analysis-of-covariance for primary variable with baseline as covariate and treatment, center and subgroup as factors. An a priori ordered testing procedure controlling the multiple α -level of 5 % will be carried out:

1) $H_{o:} \mu_E = \mu_P \text{ vs. } H_1: \mu_{E \neq} \mu_P.$

In case of a significant result for this first hypothesis two further hypotheses regarding the subgroups "sprains" and "contusions" will be

Teikoku Chemical Co. L Clinical Study Protocol :	td TK-254R-0201	Confidential Final Version 3.0	Page 11
	then be also teste model to the 5 %	ed by means of the same baselir level.	ne adjusted ANCOVA

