9.4 Populations for analysis

- Full Analysis Set The Full Analysis Set will be all randomized patients who received at least one dose of study drug. The FAS population will be primary population for the analysis of efficacy. Any exclusions from the FAS population will be made and documented before unblinding (e.g. never used study medication, randomized twice). Additional secondary populations may be defined before unblinding and will be described in detail in the SAP.
- Safety Set The safety set (SAF) will include all randomized patients who received at least one dose of the study drug. Safety will be analyzed in this population.

Before the study is unblinded, each actual post-baseline visit will be mapped to the target visit time to which it is chronologically closest. This corresponds to the following visit windows: Visit 2 (Hours 12), Visit 3 (Hours 22-24), Visit 4 (Hours 44-52), Visit 5 (Hours 68-76), Visit 6 (Hours 92-100), Visit 7 (Hours 168+). The numbering of the actual visits (from Visit 1 to Visit 7) will then be changed as needed to improve the correspondence of the actual visit times to the protocol-specified schedule. Final determinations will also be made and documented before the study is unblinded to address visits that are equidistant to two nominal visit times (Hours 12, 24, 48, 72, 96, 168) or any other irregularities.

Before the study is unblinded, the timing of the diary assessments will be reviewed, and assessments will be reclassified into time slots as appropriate to ensure that all assessments in a given comparison were made a comparable amount of time after start of treatment.

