In case of a significant result for this first hypothesis two further hypotheses regarding the subgroups "sprains/strains" and "contusions" will be then be also tested by means of the same baseline adjusted ANCOVA model to the 5 % level.

2a) H_{o:} μ_{E(spr/str)}=μ_{P(spr/str)} vs. H₁: μ_{E(spr/str)≠}μ_{P(spr/str)} in the subgroup "Sprains/strains",
2b) H_{o:} μ_{E(con)}=μ_{P(con)} vs. H₁: μ_{E(con)≠}μ_{P(con)} in the subgroup

"contusions". The primary analysis population is the Full Analysis Set (FAS).

Other important secondary efficacy outcomes are pain-on-movement on VAS at 12, 24, 48, 72, 96 and 168 hours after initiating treatment in the FAS population. These will be analyzed with

an analysis-of-covariance (ANCOVA) model and center and subgroup as main effects which will be more detailed described in the Statistical Analysis Plan (SAP). All other continuous efficacy outcomes will be analyzed based on the same model (excluding the baseline covariate when there is no appropriate baseline).

Differences between treatments on categorical outcomes will be tested with Cochran-Mantel-Haenszel tests of treatment mean ridits or of general association, stratified by center.

Figures will show the time course of outcomes by treatment group for key quantitative outcomes. The primary outcome will also be summarized by center (if there is evidence of a treatment-by-center interaction), sex, age and race but without formal statistical comparisons of treatments.

For quantitative outcomes assessed (POM, pain at rest) each null hypothesis will be tested with an analysis-on-covariance (ANCOVA) model including treatment group and center as main effects, and the baseline value as covariate (those outcomes for which there is a baseline). The model will be fit both with and without the treatment-by-center interaction. The primary model will be the model without the interaction. If the treatment/center interaction is statistically significant (p<0.05), additional ANCOVAs will be run to identify the center(s) driving the interaction and to lay out the evidence for efficacy among the centers whose results are concordant and centers driving the interaction. ANCOVA outputs will be presented in the Statistical Appendix for the primary and various secondary outcomes to allow an outside reviewer to assess the acceptability of the primary statistical model.

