6 SAMPLE SIZE

The calculation of 90 per treatment group is based on the following assumptions and considerations:

- Primary efficacy outcome is the change from baseline for POM at 72 hours after initiating treatment.
- Two-sided t-test situation with $\alpha = 5\%$.
- Assuming SD = 20 mm, the sample size provides approximately 80% power to detect a difference of 10 mm between two treatment groups if 64 patients per group are analysed.
- However, the sample size will be stipulated to n=90 per group in order to power also the two subgroup comparisons.
- Moreover, the sample size will be a total of 200 patients because a dropout-rate of approximately 10 % is taken into account.

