14.2 Analysis populations

The following analysis populations will be used for analysis of study data:

Safety population: The safety population will include all randomized patients who received at least one dose of the IMP. Safety (e.g., AEs) will be analyzed in this population.

Full Analysis Set (FAS): The Full Analysis Set (FAS) will be all randomized patients who received at least one dose of IMP. The FAS population will be primary for the analysis of efficacy. Any exclusions from the FAS population will be made and documented before unblinding (e.g. never used IMP, ankle is not sprained, randomized twice). The Intention to treat (ITT) population is identical to the Full Analysis Set (FAS).

Per protocol (PP) population: The Per protocol (PP) population will include all patients who are randomized to the clinical trial, satisfy all of the inclusion/exclusion criteria, receive the correct IMP (as randomized), have efficacy data at the 72 hours assessment, with an adhesion score of 0, 1, 2, have taken no pain medication and have no other major protocol violations as defined during a blinded review meeting.

Moreover, the PP population for the adhesion analysis (PP-PA) will include all TDS except those that were intentionally removed early in the study (e.g. because of unacceptable irritation) or those that were on patients who discontinued use of the TDS before the end of the labeled duration of wear for reasons unrelated to adhesion (e.g. because of a protocol violation). The exclusions from the PP-PA population will be described in detail in the CSR. All exclusions will be discussed in the Blind Review Meeting before DBL.

CRMB	Trial Substance:	Esflurbiprofen Hydrogel Patch	Study No.: EudraCT No.:	TK-254R-0201 2020-005165-14
	Short Title:	Local symptomatic and short-term treatment of pain in acute strains, sprains or bruises of the extremities following blunt trauma	Sponsor: TEIKC	DKU SEIYAKU CO LTD.

Only the outcomes regarding primary and secondary efficacy variables will be analyzed using this clinical trial population.

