14.4 Efficacy

14.4.1 Primary efficacy variable

Change from baseline in pain-on-movement (POM) at injured site in mm measured using a 100 mm Visual Analogue Scale (VAS) to Visit 5 (72 hours after commencement of study treatment)

The analysis of the primary endpoint will be adjusted for baseline values. The baseline adjusted difference between active treatment and placebo at 72 hours should be > 10 mm. Magnitude of reduction in pain will be used to determine 'responder rate'.

For the primary variable an analysis-of-covariance (ANCOVA) with baseline as covariate and treatment, center and subgroup as factors will be carried out. A closed testing procedure controlling the multiple α -level of 5 % will be used in the analysis:

1) H₀: $\mu_E=\mu_P$ vs. H₁: $\mu_E\neq\mu_P$. In case of a significant result for this first hypothesis two further hypotheses regarding the subgroups "sprains/strains" and "contusions" will be then be also tested by means of the same baseline adjusted ANCOVA model to the 5 % level. In case of significance, the following subhypotheses are simultaneously tested at the 5 % level of significance.

2a) H₀: $\mu_E(\text{spr/str})=\mu_P(\text{spr/str})$ vs. H₁: $\mu_E(\text{spr/str})\neq\mu_P(\text{spr/str})$ in the subgroup "Sprains/strains",

2b) H₀: $\mu_E(con) = \mu_P(con)$ vs. H₁: $\mu_E(con) \neq \mu_P(con)$ in the subgroup "contusions".

CRMB	Trial Substance:	Esflurbiprofen Hydrogel Patch	Study No.: TK-254R-0201 EudraCT No.: 2020-005165-14
	Short Title:	Local symptomatic and short-term treatment of pain in acute strains, sprains or bruises of the extremities following blunt trauma	Sponsor: TEIKOKU SEIYAKU CO LTD.

The primary analysis population is the Full Analysis Set (FAS).

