14.7 Multiplicity

A closed test procedure will be carried out for the primary variable. Therefore, no α -adjustments are necessary. The multiple level of $\alpha = 5$ % is controlled by this procedure.

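### The plan says 90 per group also powers the two subgroup tests, but on its own inputs each has at best about 65% power (70% if all 200 are analysed), and both together 42% (49%)

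*Protocol*

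**What the plan says.** Protocol 9.9, the synopsis (Statistical Considerations) and SAP 6 carry the same argument. For a two-sided 5% t-test on the 72-hour change in pain on movement, with SD 20 mm and a difference of 10 mm, 64 analysed patients per group give about 80% power. The next step is the one at issue: "However, the sample size will be stipulated to n=90 per group in order to power also the two subgroup comparisons". Enrolment then rises to 200 in total to allow for roughly 10% dropout.

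The subgroup comparisons are formal tests. Protocol 9.7.2 introduces them so: "In case of a significant result for this first hypothesis two further hypotheses regarding the" subgroups sprains/strains (2a) and contusions (2b). SAP 14.4.1 says "the following subhypotheses are simultaneously tested at the 5 % level of significance", and SAP 14.7 places them under multiplicity control: "A closed test procedure will be carried out for the primary variable". SAP 14.4.2, by contrast, treats tests of secondary variables as exploratory.

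The primary population can exceed 90 per group, because Protocol 9.4 defines it broadly: "The Full Analysis Set will be all randomized patients who received at least one dose of study drug". SAP 14.2 agrees.

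The visible text gives no expected split between the injury types, no subgroup effect or SD, no subgroup power target and no subgroup calculation.

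**The concern.** Powering the subgroup comparisons is the only reason given for going from 64 to 90 per group, since dropout is handled in a separate step. But each subgroup test rests on the patients with that injury type, so the 90 are divided. If one comparison needs 64 per arm for 80% power, two comparisons on separate patients need twice that.

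The consequence lies in how a mixed result would be read. Suppose the patch works equally well in both injury types. With the subgroup powers found below, one significant and one non-significant subgroup is about as likely as two significant ones at 90 per arm. A reader told that the trial was sized for both tests could take the non-significant one as evidence of no benefit in that injury type. The sample-size sections give no warning of this.

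**Working it through.** **Inputs.** Difference 10 mm, SD 20 mm, two-sided 5%, and 64, 90 and 100 per arm (Protocol 9.9; SAP 2 and 6). Each subgroup test is at 5% after a significant overall test (SAP 14.4.1).

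**Assumed, because the plan does not say.** The same 10 mm and SD 20 mm in each subgroup; the plan's 80% as the benchmark; a subgroup split, shown over a range.

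**Formula.** For n per arm, the noncentrality is 10 / (20 × √(2/n)), with 2n − 2 degrees of freedom. Power is the probability that a noncentral t variable exceeds the two-sided 5% critical value in absolute size.

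**The plan's own figures.**
- n = 64: noncentrality 2.83, critical value 1.979, power 80.1%. This reproduces the plan.
- n = 90: noncentrality 3.35, power 91.6%. n = 100: noncentrality 3.54, power 94.0%.
- Dropout: 90 / 0.9 = 100 per group, 200 in total. This also reproduces.

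**Subgroups, even split.**
- 90 per arm analysed, so 45 per arm in each subgroup: noncentrality 2.37, critical value 1.987, power 65.0%. The subgroups contain different patients, so power for both is 0.650 × 0.650 = 42.3%.
- All 200 analysed, so 50 per arm in each subgroup: noncentrality 2.50, power 69.7%. Both: 0.697 × 0.697 = 48.6%.

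**Other splits.**

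| Per arm analysed | Split per arm | Larger subgroup | Smaller subgroup | Both |
|---|---|---|---|---|
| 90 | 45 / 45 | 65% | 65% | 42% |
| 90 | 54 / 36 | 73% | 55% | 40% |
| 90 | 60 / 30 | 78% | 48% | 37% |
| 90 | 63 / 27 | 80% | 44% | 35% |
| 100 | 50 / 50 | 70% | 70% | 49% |
| 100 | 60 / 40 | 78% | 60% | 46% |

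A search over every split of 90 and of 100 per arm shows that the weaker subgroup's power and the joint power both peak at the even split.

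**With the overall test as gate** (simulation, even split).

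| Per arm | Each | Both | Exactly one | At least one |
|---|---|---|---|---|
| 90 | 64% | 42% | 43–44% | 86% |
| 100 | 69% | 49% | 41% | 89–90% |

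**What 80% in each subgroup would take, at an even split.**
- Patients: 2 × 64 = 128 per arm, 256 analysed. At 10% dropout, 128 / 0.9 = 142.2, so 143 per arm or 286 enrolled.
- Or a true difference of 11.9 mm (45 per arm per subgroup) or 11.3 mm (50).
- Or an SD of 16.7 mm (45) or 17.7 mm (50). If 20 mm is the unadjusted SD, the adjusted SD is 20 × √(1 − r²), so the correlation r of baseline with outcome would have to be about 0.55 or 0.47.

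**The case against.** The strongest reply is that no stated number is wrong. The plan names no subgroup power target, and the 80% benchmark and the split are supplied here. The increase does help: on the same inputs and an even split, 64 per arm leaves 32 per arm in each subgroup and about 50% power, against 65% at 90. That is true. But 80% is the only benchmark in the section, and a claim to power a comparison, placed directly after it, will be read against it. If a lower target was meant, the plan has to state it.

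The second reply is that 2a and 2b use a baseline-adjusted ANCOVA, which may be more precise than the t-test behind the calculation. This also has substance. If 20 mm is an unadjusted SD, illustrative correlations of 0.3, 0.4 and 0.5 (assumptions; the documents give none) would give 69%, 73% and 77% per subgroup at 45 per arm, and 74%, 77% and 82% at 50. Only the last reaches 80%, and power for both stays at or below 67%. The plan takes no credit for such a gain and does not say whether 20 mm is already a residual SD.

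The text could also mean subgroup contrasts from one model with pooled error. That moves 65.0% only to 65.5%.

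Finally, this is a Phase II proof-of-concept trial, its overall test is well powered, and at least one subgroup test succeeds in 86% to 90% of cases. This limits the weight of the point but does not make the sentence correct.

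**Conclusion.** The concern holds. On 10 mm, SD 20 mm and a two-sided 5% test, 90 per group does not power both subgroup comparisons at the level the plan uses for the overall one. At the even split the shortfall is about 15 percentage points per subgroup (65% against 80%), or about 10 if all 200 are analysed (70%). An uneven split makes it worse for the smaller subgroup.

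The result assumes equal effect and SD in the two injury types, the unadjusted t-test of the plan's own calculation, and 80% as the benchmark. It does not touch the primary comparison or the control of the 5% level. This is a sample-size statement that should be corrected, not a fault in the tests.

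**What to change.** Replace the sentence in Protocol 9.9, the synopsis and SAP 6 with the actual figures, for example:

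> With 90 (100) patients per group analysed, the overall test has about 92% (94%) power. If patients divide evenly between sprains/strains and contusions, with a 10 mm effect and SD 20 mm in each, an unadjusted t-test has about 65% (70%) power in each subgroup and about 42% (49%) in both. An uneven split lowers power in the smaller subgroup. A non-significant result in one subgroup is not evidence of no effect there.

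If the sponsor relies on baseline adjustment, a larger effect or a lower target, that assumption and the resulting power should be stated instead.

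Optional: report the treatment-by-subgroup interaction estimate with its 95% confidence interval beside 2a and 2b. This helps readers with a mixed result, but the correction does not depend on it.

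The cost is one sentence in three places, with no extra patients and no change to the tests. The stated subgroup power becomes less favourable. Changing the protocol text needs a written amendment under Protocol 11.1; the SAP can be corrected before it is finalised after the blind review meeting (SAP 1).

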9.10 Interim analysis

No interim analysis will be conducted.

10 Ethical considerations

10.1 Regulatory and ethical compliance

This clinical study is designed and shall be implemented and reported in accordance with the ICH Harmonized Tripartite Guidelines for Good Clinical Practice [European Medicines Agency 2006], with applicable local regulations (including European Directive 2001/20/EC, US Code of Federal Regulations Title 21, and Japanese Ministry of Health, Labor, and Welfare), and with the ethical principles laid down in the Declaration of Helsinki.

10.2 Informed consent procedures

Eligible patients may only be included in the study after providing written (witnessed, where required by law or regulation), IRB/IEC/REB-approved informed consent, The patient must indicate assent by personally signing and dating the written informed consent document or a separate assent form. Informed consent must be obtained before conducting any study-specific procedures (i.e., all of the procedures described in the protocol). The process of obtaining informed consent should be documented in the patient source documents.

Clinsearch will provide to investigators in a separate document a proposed informed consent form that complies with the ICH-GCP guideline and regulatory requirements and is considered appropriate for this study. Any changes to the proposed consent form suggested by the Investigator must be agreed to by Clinsearch/Teikoku before submission to the IRB/IEC/REB, and a copy of the approved version must be provided to the monitor after IRB/IEC/REB approval.

Women of child bearing potential should be informed that taking the study medication may involve unknown risks to the fetus if pregnancy occurs during the study and agree that in order to participate in the study they must adhere to the contraception requirement for the duration of the study. If there is any question that the patient will not reliably comply, they should not be entered in the study.

10.3 Insurance

CRMB will procure insurance for every patient enrolled in the clinical study in line with applicable regulatory requirements. Every patient will receive an information sheet on insurance coverage together with the patient information.

10.4 Responsibilities of the Investigator and IRB/IEC/REB

The protocol and the proposed informed consent form must be reviewed and approved by a properly constituted Institutional Review Board/Independent Ethics Committee/Research Ethics Board (IRB/IEC/REB) before study start. A signed and dated statement that the protocol and informed consent have been approved by the IRB/IEC/REB must be given to Clinsearch before study initiation. Prior to study start, the Investigator is required to sign a protocol

signature page confirming his/her agreement to conduct the study in accordance with these documents and all of the instructions and procedures found in this protocol and to give access to all relevant data and records to Clinsearch monitors, auditors, Quality Assurance representatives, designated agents of Clinsearch, IRBs/IECs/REBs, and regulatory authorities, as required.. Patient privacy and data confidentiality will be observed according to the applicable regulatory requirements and/or local laws.

If an inspection of the clinical site is requested by a regulatory authority, the Investigator must inform Clinsearch immediately that this request has been made. SAEs will be reported by the Investigator to the IRB/IEC/REB, as required.

